10.6 End of Study (26+/-4 weeks post scan)

The treating physician will complete the Management Plan Questionnaire to document the actual treatment given, including any changes to radiation, surgery, or medications given.

The following data from Visit 2 through to 6 months after the ¹⁸F-fluciclovine PET/CT will be abstracted from the Subject's medical record:

1. All PSA results.
2. All biopsy results and reports.
3. Restaging procedure results (e.g. bone scan or CT/MRI scans).
4. Current prostate cancer status and date of recurrence if applicable.
5. Adverse events reported by the patient
6. Date and cause of death if applicable.

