3.2 Secondary Objectives

1. To measure the fraction of patients for whom ^{18}F -fluciclovine PET/CT leads to a change of actual management by comparison with the intended management plan before ^{18}F -fluciclovine PET/CT.
2. To estimate the fraction of patients in whom ^{18}F -fluciclovine PET/CT yields evidence of recurrent disease on the basis of imaging results.
3. To estimate 1) the rates of detecting regionally recurrent disease (i.e., prostatic bed-only and/or pelvic disease outside of the bed) and 2) the rate of detecting distant metastases (i.e., bone metastases, visceral metastases, or non-regional nodal metastases) with ^{18}F -fluciclovine PET/CT in the study population.
4. To determine 1) the PPV of ^{18}F -fluciclovine PET/CT to detect regionally recurrent disease and 2) the PPV of ^{18}F -fluciclovine PET/CT to detect distant metastases in the study population in patients who undergo optional biopsy of ^{18}F -fluciclovine PET/CT findings or have documentation of disease status based on other imaging and/or follow-up data. For soft tissue disease these calculations will be limited to those patients who undergo a confirmatory biopsy and for bone disease those with confirmatory findings on MRI any time during the 6-month follow up. The denominator for the analysis will be [lesions biopsied + bone lesions].
5. To explore differences in estimated cost of treatment plans determined prior to and following ^{18}F -fluciclovine PET/CT.

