4 STUDY DESIGN

4.1 Study Overview

This prospective study will enroll up to 330 men with PSA-persistent or PSA-recurrent prostate cancer after curative-intent primary therapy and negative or equivocal findings on standard-of-care imaging (see enrolment criteria for details of eligibility). Consenting participants will be imaged with ^{18}F -fluciclovine PET/CT. Site clinicians will manage study subjects per standard practices and will document any change in treatment based on review of ^{18}F -fluciclovine PET/CT findings. Additionally, as clinically indicated, optional biopsy will be performed. All participants will be followed for up to 6 months, with clinical data collected for this study: PSA measurement from scan for 6 months. An expert reader will provide guidance to local readers on request. The final reporting of the PET/CT scan will be a single report by the local reader following any such discussion.

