5.2 Secondary Efficacy Endpoints

1. Per-patient impact (yes/no) of ^{18}F -fluciclovine PET/CT on pre-PET intended versus post-PET actual patient management (assessed at 6 months post scan)

2. The rate of detection of any disease site by ^{18}F -fluciclovine PET/CT in the study population;
3. The rate of detection of 1) prostatic bed and other pelvic disease and 2) distant metastases (i.e., bone metastases, visceral metastases, or non-regional nodal metastases) with ^{18}F -fluciclovine PET/CT in the study population;
4. The PPV of ^{18}F -fluciclovine PET/CT to detect regionally recurrent disease compared to biopsy in those patients who undergo a regional disease biopsy on the basis of a ^{18}F -fluciclovine PET/CT finding or in case of bony disease a correlation with MRI or biopsy.
5. The PPV of ^{18}F -fluciclovine PET/CT to detect distant disease compared to biopsy in those patients who undergo a distant disease biopsy on the basis of a ^{18}F -fluciclovine PET/CT finding or in case of bony disease a correlation with MRI or biopsy.

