Actual Management Plan. At the final follow up visit any deviations or changes to the Revised Management Plan will be documented

9. Biopsy

Biopsy is not required by the protocol; however patients with PET/CT positive findings in soft-tissue supported by anatomical abnormalities on CT or MRI may have a biopsy performed per standard practice where the procedure is deemed clinically feasible and safe. Biopsies completed within 4 months after imaging will contribute to the aim of the study.

1. Biopsy results of suspected bone metastases conducted per standard practice will also be collected. Bone lesions may be followed up through imaging where biopsy is not practical.
2. Based on local-radiologist/nuclear medicine physicians assessment of ¹⁸F-fluciclovine PET/CT-positive findings supported by anatomic abnormalities, conduct imaging-guided biopsy of soft-tissue ¹⁸F-fluciclovine -enhancement region per institutional standard of care;
3. Submit pathology report(s) to the ACR Core Laboratory. The address is given in the Imaging Manual.

10. Blood Chemistry Profile

Blood will be obtained and sent to each site's clinical chemistry lab for determination of serum sodium, potassium, calcium, chloride, BUN, creatinine, glutamic oxaloacetic transaminase (SGOT/AST), glutamic-pyruvic transaminase (SGPT/ALT), alkaline phosphatase, creatine kinase (CK), lactate dehydrogenase (LDH), albumin, total protein, total bilirubin.

11. Hematology

Blood will be obtained and sent to each site's clinical hematology lab for a complete blood count (hemoglobin, hematocrit, red blood cell count, white blood cell count, white blood cell differential, and platelet count determinations).

12. Urinalysis

Prior to the ¹⁸F-fluciclovine dosing a midstream sample of urine will be obtained and tested by dipstick for leukocytes, nitrite, pH, protein, ketones, glucose, bilirubin, urobilinogen, and blood. This will not be repeated following scanning unless clinically indicated.

13. Adverse Events

See Section 12.

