14.2 Analysis of Secondary Endpoints

For the evaluation of the secondary endpoint examining actual impact on therapy, questionnaires obtained pre-FACBC will be compared to treatment executed post-¹⁸F-fluciclovine PET/CT to calculate the fraction of cases with a change in management (versus no change in planned management). For the estimation of detection rate, the proportion of the ¹⁸F-fluciclovine -PET/CT positive results, 95% confidence interval will be calculated using the Exact method for a binomial distribution.

For each patient a comparison will be made of the results of the ¹⁸F-fluciclovine PET/CT results, any histopathology results, results of any other imaging and also for the clinical response to treatment(s) (standard of truth) by an Adjudication Panel. The PPV, NPV, sensitivity and specificity will be calculated, where possible, at lesion or regional or patient level. The PPV will be calculated separately for patients undergoing optional biopsy for (1) regional disease and (2) distant disease. The 95% confidence interval will be calculated using the Exact method for a binomial distribution. The Adjudication Panel will follow the Adjudication Manual that will prospectively document the processes to be used to determine a decision concerning the result of the ¹⁸F-fluciclovine PET/CT scan vs standard of truth.

Rates of disease detection (radiographic only and confirmed by pathology or MRI) will be described

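### The first secondary endpoint, PET/CT impact on actual management, has no timing or attribution limit, and the SAP analyses it against a different comparator

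*Protocol*

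**What the plan says.** **Objective.** Protocol 3.2 item 1 asks for the fraction of patients in whom PET/CT "leads to a change of actual management by comparison with the intended management plan before" the scan. The wording is causal and the comparator is the pre-scan plan.

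**Endpoint and rule.** Protocol 5.2 item 1 makes this a per-patient yes/no impact of PET/CT on "pre-PET intended versus post-PET actual patient management (assessed at 6 months post scan"). Protocol 14.2 compares the pre-scan questionnaire with the treatment carried out after the scan "to calculate the fraction of cases with a change in management (versus no change in planned management").

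**Data source.** At the End of Study contact (Protocol 10.6, 26±4 weeks) the physician is to "document the actual treatment given, including any changes to radiation, surgery, or medications given". Protocol 9.2 describes the same step against a different reference: "At the final follow up visit any deviations or changes to the Revised Management Plan will be documented".

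**SAP.** SAP 5.2 repeats the intended-versus-actual variable. The only analysis given for it, SAP 5.4.2.1, reports the share of the Evaluable Analysis Set whose actual management departed from the revised plan to a clinically significant degree. That degree is not defined. SAP 3.5, which lists changes from the protocol's analysis, mentions only the reference standard for PPV.

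**The concern.** An endpoint called PET/CT impact should count men whose treatment differed because of the scan. As written, the protocol counts men whose treatment differed from the intended plan at any time up to the six-month form, whatever the reason. Consider a man who receives exactly what was intended and has a drug added at month 5 for a rising PSA. Read literally, he is an impact case. There is no control arm from which to estimate and subtract such changes.

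The events are not remote. Protocol 10.6 collects the date of recurrence over the same period, and SAP 5.4.2.4 classifies PSA progression in the same follow-up. Elsewhere the protocol does set limits: 9.2 rules that follow-on diagnostic procedures are not a management change, and 10.5 confines the revised plan to days 2 to 22. Actual management has neither kind of limit.

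At stake are the meaning of the first secondary result and its comparison with the primary, intended-change fraction.

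**Working it through.** **1. What each rule counts.** The cases are hypothetical. The last column is the rule proposed under the fix.

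| Case | Protocol 14.2, read literally | SAP 5.4.2.1 | First course vs intended plan |
|---|---|---|---|
| Plan changed after the scan, revised plan delivered | Change | Not counted | Change |
| Plan unchanged and delivered; drug added at month 5 for rising PSA | Change | Counted if judged clinically significant | No change; listed separately |
| Plan changed after the scan, but the original plan delivered | No change | Counted if judged clinically significant | No change; listed as a deviation |
| Plan unchanged, delivered, nothing later | No change | Not counted | No change |

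The first row is the case that the objective is about, and the SAP analysis does not count it. The second row is the contamination, and it can enter under both documents' rules.

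**2. The plan's own figures.** The documents give no planning figure for this endpoint, so the inputs below come from the primary aim (Protocol 14.4): 40% positive scans, 30% change of intended plan among positive scans, 89 positive patients. These figures reproduce:
- Clopper-Pearson at 0.30 with n = 89: 0.207 to 0.406, width 0.199.
- 89 / 0.40 = 222.5, so 223 patients.
- With 248 patients, the probability of at least 89 positives is 0.918, which meets the stated 90%.
- 248 / 0.85 = 291.8, so 292.

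**3. Illustration under the protocol rule.** Let p be the true share with a scan-driven change. Let u be the share of the remaining men with an unrelated later change by the form date. The documents do not give u.

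Reported fraction = p + (1 − p)u, so the excess is (1 − p)u.

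For all men, p = 0.40 × 0.30 = 0.12, assuming no change in PET-negatives. Intervals are exact 95%.

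| Population | p (interval without contamination) | u | Excess | Reported (interval) |
|---|---|---|---|---|
| PET-positive, n = 89 | 30% (20.7–40.6) | 5% | 0.70 × 0.05 = 3.5 points | 33.5% (23.8–44.3) |
| PET-positive, n = 89 | 30% (20.7–40.6) | 10% | 0.70 × 0.10 = 7.0 points | 37.0% (27.0–47.9) |
| All, n = 248 | 12% (8.2–16.7) | 5% | 0.88 × 0.05 = 4.4 points | 16.4% (12.0–21.6) |
| All, n = 248 | 12% (8.2–16.7) | 10% | 0.88 × 0.10 = 8.8 points | 20.8% (15.9–26.4) |

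**4. Comparison with the primary fraction.** Some scan-driven plan changes will not be carried out. If a share r of them reverts to the intended plan, the reported fraction is approximately p(1 − r) + (1 − p)u, with p now the intended-change share. At p = 0.30, u = 5% and r = 20%, this is 0.240 + 0.035 = 27.5%, below 30%. At u = 10% and r = 30%, it is 0.210 + 0.070 = 28.0%. A figure near or below the primary result therefore does not show that contamination is absent.

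**The case against.** A reader might infer that the six-month form captures every treatment change and that later-line and toxicity-driven changes are in fact scored as PET/CT impact, so that the reported endpoint is inflated. The documents do not support that much.

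- **The SAP analysis differs.** Protocol 14 says that the SAP will hold any modification to the analysis. SAP 5.4.2.1 would count a month-5 addition, if at all, as a departure from the post-scan plan. The formula in step 3 is therefore not what the SAP would report. This stands. It does not rescue the endpoint, because SAP 5.2 still names intended versus actual, SAP 3.5 declares no change, and the SAP fraction answers another question.
- **Recording is not scoring.** Protocol 9.2 and 10.6 say what is written down, and full capture is needed for any version of the endpoint. The questionnaire is not in the documents, so a reason field cannot be ruled out. Attribution wording also exists: 3.2 is causal, and 4.1 says that site clinicians "will document any change in treatment based on review of" the scan findings. This stands too, but neither Protocol 14.2 nor SAP 5.4.2.1 turns attribution into a scoring rule.
- **The 30% is a narrow figure.** It is the expected change of intended plan among positive scans, not of treatment given among all men. For that reason both bases are shown.
- **Net direction is open.** Changes that are not carried out lower the fraction relative to the primary. Those men are correctly not changes in actual management. The misattributed men are the error, and that error runs only from no to yes.

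The endpoint is also descriptive and untested, which limits the consequence.

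**Conclusion.** The point holds in limited form. Protocol 5.2 item 1 and 14.2 set no limit of time, line of therapy or cause on what counts as PET/CT impact, so unrelated later treatment could be counted. SAP 5.4.2.1 replaces the comparator without declaring it and uses an undefined threshold. Its fraction would describe departures from the post-scan plan, into which the same later changes can fall, and would not estimate the stated objective.

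The size is unknown. The illustration of +3.5 to +7.0 points (PET-positive men) or +4.4 to +8.8 points (all men) rests on an assumed u of 5% to 10%, on the protocol's 40% and 30% planning figures carried over to treatment given, and, for all men, on no change in PET-negatives. It applies to the protocol rule only. It cannot be concluded that the endpoint will be inflated by any particular amount, or that the actual-change fraction will exceed the intended-change fraction.

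The primary endpoint rests on the revised plan at days 2 to 22, so it and the sample size are unaffected.

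**What to change.** In Protocol 5.2 item 1 and 14.2 and in SAP 5.4.2.1:

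1. Define actual management, for this endpoint, as the first prostate cancer treatment course started after the scan, with all its planned components, derived from the therapy dates already collected (Protocol 9.2 item 1, SAP 4.4.4).
2. Compare it with the pre-scan intended plan, using the change categories of SAP 5.4.1, and report the fraction with an exact 95% interval.
3. Move deviations from the revised plan to a separate table, and define clinically significant if the term is kept.
4. Put treatments started or altered after the first course in another separate table. Label neither table as PET/CT impact.
5. Split these tables by reason only where a reason is recorded. Dates alone cannot separate PSA failure, toxicity and patient choice, and a later choice may itself reflect the scan.
6. If a revised-plan comparator is retained for any analysis of this variable, declare it in SAP 3.5.

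The cost is wording plus one derivation, with no new visits. The downsides are some judgement on which components belong to the first course, including alterations made while it is under way, which should be settled before database lock, and possibly a lower reported fraction.

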10.7 Off Study Criteria

Subjects will not continue with the study based on the following criteria:

- Subject withdraws consent.
- Subject does not complete ¹⁸F-fluciclovine PET/CT imaging

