5.3 Safety Evaluations

1. Change from baseline QTc intervals and any clinically significant alterations in EKG after ^{18}F -fluciclovine PET/CT scanning
2. Change from baseline values in hematology and biochemistry profiles after ^{18}F -fluciclovine PET/CT scanning
3. Incidence of adverse events occurring after the ^{18}F -fluciclovine injection

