12.2 Serious Adverse Event (SAE)

An SAE is defined as any adverse event occurring at any dose that results in any of the following outcomes:

- death
- a life-threatening adverse experience
- inpatient hospitalization or prolongation of existing hospitalization
- a persistent or significant disability/incapacity
- a congenital anomaly/birth defect

Other important medical events may also be considered an SAE when, based on appropriate medical judgment, they jeopardize the subject or require intervention to prevent one of the outcomes listed.

Serious Adverse Event Reporting

Study sites will document all SAEs that occur (whether or not related to study drug) on an SAE Report Form. The collection period for all SAEs will begin after informed consent is obtained and end after procedures for the final study visit have been completed.

All SAEs following ^{18}F -fluciclovine PET/CT must be reported on the SAE reporting form within 24 hours of the Site Study Team becoming aware of the event. All SAE information must be recorded on an SAE form and faxed, or scanned and emailed to:

Blue Earth Diagnostics

SAE E mail: [contact]

[contact]

[contact]

Additional and further requested information (follow-up or corrections to the original case) will be detailed on a new SAE Report Form and faxed/emailed to the same address.

In accordance with the standard operating procedures and policies of the local Institutional Review Board (IRB)/Independent Ethics Committee (IEC), the site investigator will report SAEs to the IRB/IEC.

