4 STUDY SUBJECTS

4.1 Analysis sets

The list of subjects to be included in each of the analysis sets is to be agreed between the Syne qua non statistician and Blue Earth Diagnostics once all study data are available and prior to database lock.

Enrolled Set: All subjects who entered screening.

Safety Analysis Set (SAF): All subjects who have been included in the database and have been administered ^{18}F -fluciclovine will be included in the Safety Analysis Set (SAF).

Full Analysis Set (FAS): All subjects enrolled who have had an ^{18}F -fluciclovine PET/CT scan will be included in the Full Analysis Set (FAS).

Evaluable Analysis Set (EAS): All subjects from the FAS who have an intended treatment management plan completed and a revised management plan page completed will be included in the Evaluable Analysis Set (EAS).

Per Protocol Set (PPS): All subjects in the EAS who meet the second and third protocol inclusion criteria (see protocol section 6.2) and any other subject without major significant deviation following review of the protocol deviation list.

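### Protocol 10.7 takes every subject with an incomplete scan off study, injected or not, so read literally it ends post-dose safety observation that the AE endpoint and the SAP count from injection

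*Protocol*

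**What the plan says.** Protocol 10.7 opens with "Subjects will not continue with the study based on the following criteria" and gives two criteria. One is withdrawal of consent; the other is "Subject does not complete ¹⁸F-fluciclovine PET/CT imaging". It makes no exception for a man who has already received the product.

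Other passages count from the injection. Protocol 5.3, item 3, is "Incidence of adverse events occurring after the" injection. Sections 10.3 and 10.4 time the AE checks, the later vital signs and the telephone call from injection or dosing. SAP 4.1 defines the Safety Analysis Set (SAF) as "All subjects who have been included in the database and have been administered" the product. SAP 6.1 tabulates treatment-emergent events up to 42 days after administration.

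On serious events, Protocol 12.2 states "Study sites will document all SAEs that occur (whether or not related to study drug) on an SAE Report Form" and "The collection period for all SAEs will begin after informed consent is obtained". Its 24-hour sentence is worded to the scan: "All SAEs following ^{18}F -fluciclovine PET/CT must be reported on the SAE reporting form within 24 hours".

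**The concern.** A dosed man whose scan is abandoned belongs to the safety population, but the off-study rule, taken at its word, removes him before most of his planned safety observation. The loss would not be random. An acute reaction during imaging can itself be why the scan stops, so the men most in need of observation are the ones the rule can release. At stake are the completeness of AE severity and of later events, and the post-dose laboratory and EKG values, in exactly those men.

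**Working it through.** No plan figure has to be reproduced. The check sets the passages side by side and then works through the timing and the analysis rules.

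| Item | Counted from | Place |
|---|---|---|
| Off-study criterion | completion of the scan | Protocol 10.7 |
| AE checks at 30, 60 and 120 min | injection | Protocol 10.3 |
| Vital signs at 60 and 120 min | injection | Protocol 10.3 |
| First post-scan vital signs | scan | Protocol 10.3 |
| Post-dose bloods and EKG | scan day, or within 7 days of the scan | Protocol 10.3, Appendix 1 |
| Call at 24-72 h | dosing | Protocol 10.4 |
| End-of-study abstraction of AEs and deaths | scan | Protocol 10.6 |
| AE endpoint | injection | Protocol 5.3, item 3 |
| QTc/EKG and laboratory endpoints | scanning | Protocol 5.3, items 1 and 2 |
| SAF | administration | SAP 4.1 |
| TEAE definition and 42-day window | administration | SAP 6.1 |
| 24-hour SAE reporting | scan | Protocol 12.2 |

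1. **Timing.** Imaging starts about 4 minutes after injection and lasts about 25 minutes (10.3), so it ends at about 4 + 25 = 29 minutes. With the 3-to-5-minute start allowed in 11.2, the range is 28 to 30 minutes. A scan cut short therefore stops before the 30-minute AE check. Apart from the look at the injection site after administration (8.5), the scheduled post-dose assessments all lie ahead of that man.

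2. **Does any passage exempt him?** None that could be read does. Section 10.8 retains data from withdrawn subjects whose baseline measures are complete, but does not say that safety collection continues. The same section limits discontinuation for ineligibility to the time before administration. The protocol therefore draws the dosed/undosed line there and omits it in 10.7.

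3. **Does the analysis expect him?** Yes. SAP 4.1 defines the SAF by administration and the FAS by having had a scan, so a man can be in the first without the second.

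4. **What survives.** The reaction that stops the scan is an AE under 12.1, is treatment-emergent under SAP 6.1, and is retained under 10.8 if baseline measures are complete.

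5. **What can be lost.** SAP 6.1 counts each subject once per preferred term, at the worst grade or closest relationship. If observation stops, a later rise in grade or a different event is not captured. Under SAP section 6, subjects enter the tables only if they have data, and nothing is imputed (SAP 2 and 5.4.3). Without post-dose bloods or EKG he drops out of those change-from-baseline summaries.

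6. **Direction.** Missed later events can only lower AE counts and grades. For laboratory and EKG summaries the effect is selective omission, and its direction cannot be inferred.

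7. **The 24-hour sentence.** If the word following means after the scan, an SAE between injection and the end of the scan has no clear deadline. It is still documented, because 12.2 collects all SAEs from consent. Collection ends with the final study visit, and that point is unclear for a man who leaves at Visit 2.

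**The case against.** The strongest reply is that 10.7 neither says when removal takes effect nor waives safety checks, while 10.3 and 10.4 time several of them from injection or dosing. A careful site would probably complete them. That stands as a reason to call the follow-up undefined rather than expressly cancelled. It does not settle the conflict, because the wording of 10.7 is mandatory and nothing that could be read limits it.

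The protocol also often treats scan and injection as one procedure: items 1 and 2 of 5.3 are worded to scanning. This weakens a strict reading of 12.2, where following the PET/CT may have been meant to include the injection.

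Other safeguards exist. Section 16.5 obliges investigators to report any AE to the sponsor, and 16.2 sends serious events to the IRB/IEC regardless of causality. These make it unlikely that a serious acute reaction goes unreported. They do not supply the 24-hour clock or schedule any observation.

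A reader might infer that 12.2 causes assessments to be lost. It does not; it sets a reporting deadline. A reader might also infer that the reactions themselves vanish from the AE rates, or that men without post-dose values are counted as normal. Steps 4 and 5 of the working show that neither follows.

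**Conclusion.** The point holds in a limited form. The off-study rule depends on completing the scan, whereas the AE endpoint, the timed AE checks, the call, the SAF and the TEAE window depend on the injection. Safety follow-up of a dosed man with an incomplete scan is left undefined and, on the literal reading, ended. The possible loss is informative, but it concerns the later course of the event and subsequent AE, laboratory or EKG changes, not the event that stopped the scan.

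The size cannot be computed, because the documents do not give the number of dosed men with incomplete scans. As a pure assumption, 0 to 5% of 330 men would be 0 to 16 (0.05 × 330 = 16.5). That would be the number exposed to the rule, not the number of events lost, and only some of those scans would have stopped because of a reaction. No figure for bias in AE incidence is supported.

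The 12.2 wording is a separate and smaller point. The text directly after 12.2 was not available, so a clarification there cannot be excluded.

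**What to change.** Reconcile Protocol 10.7 with 10.3, 10.4, 5.3 and SAP 4.1. State that an incomplete scan ends only the imaging and management-plan assessments, and that any dosed subject stays under the safety data collection already in the Schedule of Events. Withdrawal of consent remains its own criterion.

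Separately, reconcile the 24-hour sentence in 12.2 with the injection-based AE definitions, so that the time between injection and the end of the scan is clearly covered.

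No new SAP listing is needed. SAP 4.2 already lists withdrawal reasons, 4.5 lists all administration data, and 6.1 lists all AEs, with SAEs listed separately.

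The cost is two sentences in an amendment and at most a few extra follow-up contacts, with no new procedure.
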